Exploratory analyses will be performed to examine other questions; although, after correction for multiple comparisons, the statistical significance of these will be low, requiring future replication. Nevertheless, the patterns of amyloid deposition (from Florbetapir uptake) and brain atrophy between TBI, PTSD, and control subjects will be compared, with similar patterns from non-Veteran subjects in ADNI. These results of these studies may provide insight into the question of whether or not TBI and PTSD alter the pattern of amyloid distribution or brain atrophy. Such analyses may also give insight into the question of whether TBI or PTSD is associated with reduced cognitive reserve. The relationship between cortical areas with amyloid plaque (from amyloid PET) and underlying white matter integrity as assessed with DTI will also be studied to determine if axonal injury resulting from TBI was associated with greater amyloid accumulation, or whether regions of brain with axonal damage have less amyloid accumulation due to disconnection and reduced brain activity.

Primary Analyses: Comparing Groups on Baseline Level (Hypothesis sets 1 & 3):

Primary outcomes for these analyses include uptake on Florbetapir scans, CSF amyloid beta, CSF tau and Ptau, volumes of the hippocampus, entorhinal cortex, and parietal/temporal cortices, DTI summary measures (in the third set of hypotheses) and measures of cognitive function, including delayed episodic memory.

The analyses will begin with: 1) numerical and graphical summaries of the measures within each group to assess the underlying distribution and detect outliers or questionable values which will be flagged and checked with the sites for accuracy. 2) Analysis of variance (ANOVA) for a simple unadjusted comparison between the groups. If the global F-test for group difference is significant, there will be a follow-up with post-hoc pairwise tests, specifically between the TBI or PTSD groups and the Veteran control group, adjusted for multiple comparisons using the Bonferroni or Tukey's Honestly Significant Difference (HSD) approach. 3) linear regression models that include group as an independent variable to adjust for potential confounders including age, gender, APOe4 genotype, and alcohol dependence. Model assumptions will be assessed through graphical and numerical approaches and transformations or non-linear models will be used if suggested by the diagnostics. Hypotheses will be supported if the TBI and PTSD groups show significantly higher levels of uptake on amyloid PET scans and CSF tau or Ptau than the Veteran controls and significantly lower levels of CSF amyloid beta, MRI volumes, and cognitive function than the Veteran controls.

Primary Analyses: Comparing Groups on Annual Change (Hypothesis sets 1 & 3):

Primary outcomes for these analyses include annual change in volumes of the hippocampus, entorhinal cortex, and parietal/temporal cortices and annual change in cognitive function such as delayed recall. There will be two assessments for each person, approximately one year apart. Therefore, for each participant as a measure of annual change, there will be a construction of difference scores between the measures obtained at the follow-up visit and the baseline visit. The scores will be divided by the time between the assessments to account for variability in timing of the follow-up assessments between participants. Analyses will be similar to those described above for comparing groups on the baseline level except that the final linear regression models will also be adjusted for baseline level of the outcome measure. Hypotheses will be supported if the TBI and PTSD groups show significantly faster rates of atrophy and cognitive decline than the Veteran controls.

TBI or PTSD associated with reduction in cognitive reserve (Hypothesis set two):

The main outcomes for these analyses will be level and annual change in cognitive function, particularly memory while the predictors of interest are group, baseline hippocampal volume, and uptake from the amyloid PET scans. Linear regression methods similar to those described above will be used. Of particular interest for these analyses are the interactions between group and the imaging predictors. Power will be limited for these analyses, so results will mainly serve as support for future studies of PTSD, TBI, and cognitive reserve. However, significant interactions suggesting worse cognitive function

in the TBI or PTSD groups relative to Veteran controls at a given level of MRI, or amyloid imaging measures would support the hypotheses.

Within-group correlations to assess dose-response:

Outcomes for these analyses will be the same as those used for hypothesis sets one, two, and three. Interest lies in assessing whether the baseline levels or rates of atrophy or cognitive decline are associated with severity of TBI or PTSD. Analyses will be performed within each of those groups separately. Severity of TBI or PTSD will be the predictor of interest. Simple linear regression models that include severity of TBI or PTSD as the independent variable will be used. Multiple regression models to adjust for potential confounders including age, gender, and APOe4 genotype and alcohol dependence will be used next. As stated above for the primary analyses, model assumptions will be assessed and transformations or non-linear models will be used if suggested by the diagnostics. Secondary hypotheses will be supported if increased severity of TBI or PTSD is significantly associated with lower levels of CSF amyloid beta, MRI volumes, and cognitive function, higher levels of CSF tau or Ptau, and increased rates of brain atrophy and cognitive decline.

Exploratory Analyses:

As described earlier, exploratory analyses will be performed to examine other questions; although, after correction for multiple comparisons, power will be low requiring future replication. Nevertheless, there will be a comparison of the patterns (using voxel based methods) of amyloid deposition (from amyloid PET) and brain atrophy between TBI, PTSD, and control subjects, and with similar patterns from non Veteran subjects in ADNI. The results of these studies may provide insight into the question of whether or not TBI and PTSD alter the pattern of amyloid distribution or brain atrophy. Furthermore, the relationships between amyloid deposition, atrophy, and cognitive function may provide insight into the question of whether TBI or PTSD is associated with reduced cognitive reserve. Further exploratory analyses will assess the relationship between cortical areas with amyloid plaque (from amyloid PET) and underlying white matter integrity as assessed with DTI to determine if axonal injury resulting from TBI was associated with greater amyloid accumulation, or whether regions of the brain with axonal damage have less amyloid accumulation due to disconnection and reduced brain activity. Linear regression methods, described above, will be used to assess the association between regional measures of amyloid accumulation and axonal damage.

Power Analysis:

Power analyses are presented for each class of primary hypotheses assuming a two-sided test and were calculated using nQuery. For comparison of the TBI or PTSD group to the Veteran controls, assuming alpha = 0.025 to account for multiple comparisons and 65 individuals per group at baseline and 61 per group for longitudinal measures, there will be an 80% power to detect a difference as small as 0.55 standard deviations in level and as small as 0.56 standard deviations in rate of atrophy or cognitive decline. For example, using means and standard deviations from measures in the normal controls within ADNI-1, this difference would translate to at least a 6.7% lower hippocampal volume, and at least a 14.7% lower CSF amyloid beta. Because there is little change in the ADNI normals, differences in change will be much more difficult to detect. However, these data will provide initial estimates of how much change is experienced in the TBI and PTSD groups which will help in planning larger scale

longitudinal studies of these groups. The power analysis will be able to detect at least a doubling of the rate of hippocampal atrophy and at least a quadrupling of the rate of decline in delayed recall in the TBI or PTSD groups compared to the Veteran controls. For within group correlations, there will be an 80% power to detect a correlation as small as 0.33 with cross-sectional outcomes and 0.34 with outcomes of change.

25. Bibliography & References Cited:

- 1. Scarmeas, N. and Y. Stern, *Cognitive reserve: implications for diagnosis and prevention of Alzheimer's disease*. Curr Neurol Neurosci Rep, 2004. 4(5): p. 374-80.
- 2. Snitz, B.E., E.S. O'Meara, M.C. Carlson, A.M. Arnold, D.G. Ives, S.R. Rapp, J. Saxton, O.L. Lopez, L.O. Dunn, K.M. Sink, and S.T. DeKosky, *Ginkgo biloba for preventing cognitive decline in older adults: a randomized trial.* JAMA, 2009. 302(24): p. 2663-70.
- 3. Leoutsakos, J.M., B.O. Muthen, J.C. Breitner, and C.G. Lyketsos, *Effects of non-steroidal anti-inflammatory drug treatments on cognitive decline vary by phase of pre-clinical Alzheimer disease: findings from the randomized controlled Alzheimer's Disease Anti-inflammatory Prevention Trial.* Int J Geriatr Psychiatry, 2011.
- 4. Lyketsos, C.G., J.C. Breitner, R.C. Green, B.K. Martin, C. Meinert, S. Piantadosi, and M. Sabbagh, *Naproxen and celecoxib do not prevent AD in early results from a randomized controlled trial*. Neurology,
- Shaw, L.M., H. Vanderstichele, M. Knapik-Czajka, M. Figurski, E. Coart, K. Blennow, H. Soares, A.J. Simon, P. Lewczuk, R.A. Dean, E. Siemers, W. Potter, V.M. Lee, and J.Q. Trojanowski, *Qualification of the analytical and clinical performance of CSF biomarker analyses in ADNI*. Acta Neuropathol, 2011. 121(5): p. 597-609.
- 6. Petersen, R.C., P.S. Aisen, L.A. Beckett, M.C. Donohue, A.C. Gamst, D.J. Harvey, C.R. Jack, Jr., W.J. Jagust, L.M. Shaw, A.W. Toga, J.Q. Trojanowski, and M.W. Weiner, *Alzheimer's Disease Neuroimaging Initiative (ADNI): clinical characterization*. Neurology, 2010. 74(3): p. 201-9.
- Aisen, P.S., R.C. Petersen, M.C. Donohue, A. Gamst, R. Raman, R.G. Thomas, S. Walter, J.Q. Trojanowski, L.M. Shaw, L.A. Beckett, C.R. Jack, Jr., W. Jagust, A.W. Toga, A.J. Saykin, J.C. Morris, R.C. Green, and M.W. Weiner, *Clinical Core of the Alzheimer's Disease Neuroimaging Initiative: progress and plans*. Alzheimers Dement, 2010. 6(3): p. 239-46.

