Primary Objectives	The primary objectives to be tested are: 1. Veterans without mild cognitive impairment (MCI)/dementia, with a history of moderate to severe TBI during military service (but no PTSD), as well as Veterans without MCI/dementia, with ongoing PTSD (but no TBI) have increased evidence for AD pathophysiological markers, when compared with Veteran controls (without TBI, PTSD, MCI/dementia, and also matched for age, APOE4 status, and accounting for other comorbidities) as measured by: a. Greater uptake on Florbetapir F18 amyloid PET scans b. Lower CSF amyloid beta levels c. Increased CSF tau/P tau levels d. Greater brain atrophy in hippocampus, entorhinal cortex, and parietal/temporal cortices e. Greater longitudinal rates of brain atrophy in hippocampus, entorhinal cortex, and parietal/temporal cortices f. Reduced cognitive function, especially delayed memory g. Greater rate of change of cognitive function
	 TBI and/or PTSD reduces brain reserve, causing greater cognitive impairment after accounting for age, educational status, pre-war cognitive function, as assessed with the Armed Forces Qualifying Exam score during basic training, to be measured by: Brain amyloid load or hippocampal volume. Greater cognitive impairments at a given level of brain Aβ, or Brain volume in the TBI or PTSD group than controls

- 3. TBI, when compared to controls, is associated with changes in brain regions previously reported to be associated with TBI [37-39].
 - a. White matter regions frequently noted to have reduced microstructural integrity due to TBI on DTI include the anterior corona radiata, uncinate fasciculus, corpus callosum, forceps minor, forceps major, sagittal stratum, corticospinal tract, inferior fronto-occipital fasciculus and cingulum bundle [37-
 - b. Reduced hippocampal volume in PTSD compared to controls, [32, 33-36].
- 4. There will be significant correlations between severity of TBI (from hospital records) and severity of PTSD (CAPS score) on the abovelisted outcomes, i.e. a dose response effect.
- 5. Exploratory analyses will also be performed to examine other questions, and compare the patterns (using voxel based methods) of amyloid deposition (from Florbetapir F18 uptake) and brain atrophy among TBI, PTSD, and control subjects, and with the patterns from non-Veteran subjects in ADNI. The results of these studies may provide insight into:

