	 All MRI and PET scans will be rapidly assessed for quality so that subjects may be rescanned if necessary. In the event that the scan fails the quality control procedure and cannot be used, we will repeat the Florbetapir scan. In ADNI to date, less than .5% of scans require repeat. Because of this, we include the total dose in the case of the necessity for repeating the scan once. See dosimetry table on page 62. All clinical data will be collected, monitored, and stored by the Coordinating Center at University of California, San Diego. The University of Pennsylvania will collect biomarker samples and, and NCRAD will collect genetic samples. All raw and processed image data will be archived at LONI. SFVAMC will be responsible for the mail effort, recruitment, and the telephone screeners and clinical interviews. There will be NO subjects seen on the SFVAMC campus. UCSF will be one of the ADNI sites. There will be subjects seen at the UCSF ADNI clinic and at the China Basin PET scan facility. The UCSF ADNI site will submit their own

	IRB documents, using this master template for protocol and consent forms, as will each of the selected ADNI sites.
Outcome Measures	Level of early cognitive functioning as measured by Armed Forces Qualifying Exam Score.
	2. Level of current cognitive function as measured by Cognitive tests.
	3. Prevalence of brain AD pathology (measured by amyloid PET, CSF Aβ and tau, medial temporal lobe atrophy, (after accounting for effects of age and APOE).
	Prevalence of AD pathology and other co-morbid diseases/pathology identified at autopsy.
	 5. Examine group differences for each imaging and biomarker measurements: a. Brain uptake –Florbetapir F18 amyloid PET scans b. Levels of CSF Amyloid beta, tau/P tau c. Rate of brain atrophy in hippocampus, entorhinal cortex, and parietal/temporal cortices (both current and longitudinally)
	6. Hippocampal atrophy while accounting for brain amyloid.
Sponsor	Department of Defense

Schedule of Events

	Completed by SFVAMC Recruiters and PTSD Core									
Stage of Project		Basel	line		12 Month (approximate) Follow					
Who is responsible?	SFVAMC Recruiters	PTSD Core	Self Reports	Local ADNI SITE	SFVAMC Recruiters	PTSD Core	Self Report	Local ADNI SITE		
Invitation letter, brochure, & response postcards mailed to subjects	X				X					
6 month (approximate) contact call	X									
Birthday cards/holiday cards	X			X	X			X		
Thank you cards	X			X	X			X		

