The primary hypothesis to be tested (all data analyses will be covaried for age, gender, and Apolipoprotein E (APOE) 4 genotype) are that Veterans without MCI/dementia with a history of moderate to severe TBI during military service, as well as Veterans with ongoing PTSD, have increased evidence for AD pathophysiological markers, when compared with Veteran controls (without TBI or PTSD and matched for age, APOE4 status and accounting for other comorbidities) manifested as the following dependent variables:

- Greater uptake on Florbetapir F18 amyloid PET scans;
- Lower CSF amyloid beta levels;
- Increased CSF tau/P tau levels;
- Greater brain atrophy in hippocampus, entorhinal cortex, and parietal/temporal cortices;
- Greater longitudinal rates of brain atrophy in hippocampus, entorhinal cortex and parietal/temporal cortices;
- Reduced cognitive function, especially delayed memory; and
- Greater rate of change of cognitive function.

Second Hypothesis

The second major hypothesis to be tested is that TBI and/or PTSD reduce brain reserve, causing greater cognitive impairment after accounting for age, educational status, and pre-war cognitive function as assessed with the Armed Forces Qualifying Exam score during basic training, brain amyloid load or hippocampal volume. Greater cognitive impairments at a given level of brain Aβ or brain volume in the TBI or PTSD group compared with controls would support the hypothesis of reduced cognitive reserve.

Third Hypothesis

The third hypothesis will be that TBI, when compared to controls, is associated with changes in brain regions previously reported to be associated with TBI [37-39]. White matter regions frequently noted to have reduced microstructural integrity due to TBI on DTI include the anterior corona radiata, uncinate fasciculus, corpus callosum, forceps minor, forceps major, sagittal stratum, corticospinal tract, inferior fronto-occipital fasciculus and cingulum bundle [37-39]. Previous findings of reduced hippocampal volume in PTSD compared to controls will also be replicated [32-36].

Fourth Hypothesis

The fourth hypothesis is that there will be significant correlations between severity of TBI (from hospital records) and severity of PTSD (CAPS score) on the above-listed outcomes, i.e. a dose response effect.

Exploratory Analyses

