- Clinical Dementia Rating (CDR) [63]: The CDR describes five degrees of impairment in performance on each of 6 categories of cognitive functioning including memory, orientation, judgment and problem solving, community affairs, home and hobbies, and personal care.
- Activities of Daily Living | Functional Assessment Questionnaire (FAQ) [64]: Based on an interview with a study companion or qualified partner, a subject is rated on their ability to carry out ten complex activities of daily living.
- Neuropsychiatric Inventory (NPI) [65]: The Neuropsychiatric Inventory (NPI) is a wellvalidated, reliable, multi-item instrument to assess psychopathology in AD based on an interview with a study companion or qualified partner.
- Geriatric Depression Scale [66]: The Geriatric Depression Scale (Short Form) is a selfreport scale designed to identify symptoms of depression in the elderly. The scale consists of 15 questions that the subject is asked to answer yes or no on the basis of how they felt over the past week.
- Armed Forces Qualification Test (AFQT)/Army Classification (ACT): Preinjury intelligence is a strong predictor of long term decline in many cohorts including those with Traumatic Brain Injury among these variables [25]. Preinjury intelligence [67, 68] can be estimated by the Armed Forces Qualification Test/Army Classification Test which was administered prior to the completion of basic training. As part of the ADNI cognitive battery these exact same tests will be re-administered to the subject and the difference in score of these tests will be used as a major dependent variable in data analysis. The AFQT and ACT will be used as 1) measures of cognitive reserve; 2) the change in the score from its original use in Basic Training to the time of the study will be used as an important outcome measure to test hypotheses.

17. Risks

All of the study procedures are well-established test methods, involving minimal discomfort, though there could be some risks or discomforts from being in the study. Possible risks for each procedure are discussed

Initial Screening and Clinical Interview: The screening and interview questions may be distressing to some participants. It is possible that being asked questions about mental health or traumatic military experiences may distress subject.

- Subject is free to decline to answer any question or to complete any portion of the interview or, to stop the interview at any time.

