Primary analyses involve comparing groups on baseline levels of CSF, Neuroimaging (MRI and amyloid PET), and cognitive measures associated with AD pathology and annual change in MRI and cognitive measures to assess whether PTSD or TBI is associated with increased evidence for AD compared to Veteran controls. Further analyses will focus on within-group correlations to assess a doseresponse association between outcomes and severity of PTSD or TBI and whether TBI or PTSD reduces cognitive reserve. Additional exploratory analyses will also be conducted. The specific analytic methods for hypothesis testing are listed below followed by an assessment of power.

The primary hypotheses to be tested (all data analyses will be covaried for age, gender, and APOe4 genotype) are that Veterans without MCI (or dementia, with a history of moderate to severe TBI during military service, as well as Veterans with ongoing PTSD, have increased evidence for AD, when compared with Veteran controls (without TBI or PTSD) manifested as: 1) greater uptake on Florbetapir amyloid PET scans; 2) lower CSF amyloid beta levels; 3) increased CSF tau/P tau levels; 4) brain atrophy in hippocampus, entorhinal cortex, and parietal/temporal cortices; and 5) greater rates of brain atrophy in hippocampus, entorhinal cortex and parietal/temporal cortices; 6) reduced cognitive function, especially delayed recall.

The second major hypotheses to be tested is that TBI and/or PTSD reduce brain reserve causing greater cognitive impairment after accounting for age, brain amyloid load or hippocampal volume. Greater cognitive impairments at a given level of brain A\beta or brain volume in the TBI or PTSD group compared with controls would support the hypothesis of reduced cognitive reserve.

The third hypothesis will be that TBI, when compared to controls, is associated with changes detected with DTI in brain regions previously reported to be associated with TBI [37-39].

Finally, the hypothesis that there will be significant correlations between severity of TBI (determined from medical records) and severity of PTSD (CAPS score) on the above-listed outcomes in the TBI and PTSD groups respectively will be tested.

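### Section 24 restates hypothesis 2 without the education and pre-war AFQT adjustment that the synopsis and section 5 make part of it, and names neither in its models

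*Protocol*

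**What the plan says.** **Hypothesis 2 where it is defined.** The synopsis (Primary Objectives, item 2) has TBI and/or PTSD "causing greater cognitive impairment after accounting for age, educational status, pre-war cognitive function". Section 5 (Second Hypothesis) conditions the impairment in the same way, "after accounting for age, educational status, and pre-war cognitive function as assessed with the Armed Forces Qualifying Exam score during basic training", and adds brain amyloid load or hippocampal volume.

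**Hypothesis 2 where it is analysed.** Section 24 restates it as "causing greater cognitive impairment after accounting for age, brain amyloid load or hippocampal volume". Education and AFQT are gone. The section's general rule is that "all data analyses will be covaried for age, gender, and APOe4 genotype". The regression models for baseline level are there "to adjust for potential confounders including age, gender, APOe4 genotype, and alcohol dependence". For hypothesis set two, "the predictors of interest are group, baseline hippocampal volume, and uptake from the amyloid PET scans", and the rest of the model is taken from the methods described earlier in the section. Neither education nor AFQT is named anywhere in section 24.

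**AFQT elsewhere.** Section 16 (AFQT/ACT entry) says preinjury intelligence strongly predicts later decline. It plans to use the tests as measures of reserve, and to re-administer them so that "the difference in score of these tests will be used as a major dependent variable in data analysis". Section 24 does not list that change score. The synopsis lists "Level of early cognitive functioning as measured by Armed Forces Qualifying Exam Score" as the first outcome measure, although the score dates from basic training.

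**The concern.** An analyst who follows section 24 literally fits a model for hypothesis 2 that does not test the hypothesis stated in section 5. The missing terms matter. Hypothesis 2 asks whether TBI or PTSD lowers cognition at a given level of pathology. The obvious rival explanation is that the exposed veterans scored lower before the war. Pre-war AFQT is the one measure the protocol plans to obtain that predates the exposure and speaks to that explanation.

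The design does not cover the gap. The study is non-randomized, and controls are chosen to be comparable in age, gender and education but not in AFQT. Any AFQT difference between groups that is related to current cognition would therefore enter the group main effect on cognitive level.

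**Working it through.** **1. Covariates side by side (hypothesis 2).**

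| Place in protocol | Age | Education | Pre-war AFQT | Amyloid or hippocampus |
|---|---|---|---|---|
| Synopsis, Primary Objectives item 2 | yes | yes | yes | yes |
| Section 5, Second Hypothesis | yes | yes | yes | yes |
| Section 24, restated hypothesis | yes | no | no | yes |
| Section 24, regression confounders (also gender, APOE4, alcohol dependence) | yes | no | no | not listed there |
| Section 24, hypothesis set two predictors (with group) | by reference back | no | no | yes |

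The first two rows cannot be reconciled with the last three by reading alone.

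**2. The protocol's power figure.** Inputs from section 24: 65 per group, two-sided alpha 0.025, 80% power, 0.55 SD. The noncentrality is 0.55 × √(65/2) = 0.55 × 5.701 = 3.135. The critical t on 128 degrees of freedom is 2.268. Power is 80.6% (81.4% by the normal approximation), and the smallest detectable difference is 0.546 SD. The stated figure reproduces. It contains no covariates, so it neither supports nor weakens the point, but it supplies the setting for the next step.

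**3. Illustration of bias in a group main effect on cognitive level.** The documents give neither the AFQT-cognition correlation (r) nor the AFQT gap between groups (g, in SD), so both are assumptions: r = 0.3 to 0.7 and g = 0 to 0.5. With no true group effect and AFQT left out:

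- Bias = r × g SD.
- False-positive rate = P(|T| > 2.268), where T is noncentral t on 128 df with noncentrality r × g × 5.701.

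Worked case, r = 0.5 and g = 0.3: bias 0.15 SD, noncentrality 0.855, rate 8.3%.

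| r | g = 0 | g = 0.2 | g = 0.3 | g = 0.5 |
|---|---|---|---|---|
| 0.3 | 0; 2.5% | 0.06; 3.3% | 0.09; 4.5% | 0.15; 8.3% |
| 0.5 | 0; 2.5% | 0.10; 4.9% | 0.15; 8.3% | 0.25; 20.3% |
| 0.7 | 0; 2.5% | 0.14; 7.5% | 0.21; 14.6% | 0.35; 39.5% |

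Each cell gives the bias in SD, then the false-positive rate against a nominal 2.5%. The largest bias is 0.35/0.55 = 64% of the difference the study is sized to detect.

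**4. What the table does not cover.** Section 24 says the interactions between group and the imaging predictors are of particular interest for hypothesis 2. If the AFQT gap is constant, and AFQT relates to the imaging measure with the same slope in each group, omitting AFQT adds r × g to the group term and nothing to the interaction. The table applies to the group main effect only.

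**5. Precision on cognitive level.** With AFQT in the model, the detectable difference is about 0.546 × √(1 − r²) × √(1 + g²/4). At r = 0.5 and g = 0.3 this is 0.546 × 0.866 × 1.011 = 0.478 SD. This does not carry over to annual change, where the models already adjust for the baseline level of the outcome.

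**The case against.** The strongest reply is that nothing forbids the adjustment. The confounder lists in section 24 open with the word including, section 5 remains in force, and section 24 shortens other hypotheses too: it drops the rate of cognitive change from hypothesis 1 and the hippocampal replication in PTSD from hypothesis 3. A full covariate list is often left to a statistical analysis plan. This stands to the extent that a reader might infer that AFQT will certainly be left out, and the documents do not show that. But an open list does not reconcile two statements of the same hypothesis, and it leaves open a choice that section 5 had made.

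Four further objections stand and limit the point:

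- **Other hypotheses.** A reader might infer that hypotheses 1 and 4 are contradicted as well. They are not. Only hypothesis 2 promises these covariates. Hypothesis 1 is consistently covaried for age, gender and APOE4, and hypothesis 4 is analysed within the TBI and PTSD groups, so a gap between groups does not bias it.
- **Education.** Controls are selected to be comparable in education, which partly deals with that covariate by design and may narrow an AFQT gap. AFQT is the stronger half of the point.
- **Roles of AFQT.** A reader might infer that its uses conflict throughout. A pre-war score can be a covariate for other tests and also the starting point of a change score, which itself takes account of premorbid level. What is wrong is that section 24 carries neither use, and that the synopsis labels a pre-exposure score as an outcome.
- **Weight of hypothesis 2.** Section 24 concedes limited power here and treats the results mainly as support for later studies. That lowers the stakes but does not remove the bias.

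**Conclusion.** The point holds as an internal contradiction with a plausible consequence. The models as written in section 24 do not test hypothesis 2 as the synopsis and section 5 state it. They leave unadjusted a pre-exposure variable that the protocol itself regards as strongly predictive and plans to obtain. The AFQT change score, presented in section 16 as a major outcome, has no place in the analysis section.

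The size of any bias is unknown. The range of 0 to 0.35 SD, with a false-positive rate of 2.5% to about 40%, rests entirely on the assumed correlation and gap. It includes no bias at all if the groups do not differ in AFQT, and it concerns a group main effect on cognitive level. A reader might take those rates as error rates for hypothesis 2 as a whole. The documents do not support that, because the interactions of particular interest are not biased by a constant gap. This should be fixed, but it does not invalidate the study: the scores are planned to be obtained and the models can be corrected before analysis.

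**What to change.** 1. In section 24, restore education and pre-war AFQT/ACT in the statement of hypothesis 2, and name both as covariates in the hypothesis set two models.
2. As a cheap improvement rather than a correction, add them to the hypothesis 1 regression models for cognitive level.
3. List AFQT/ACT change since basic training as a cognitive outcome in section 24. Do not put pre-war AFQT in the model for that outcome without justification, since the same score would then be on both sides.
4. In the synopsis outcome list, relabel pre-war AFQT as a baseline covariate.
5. For missing military scores, specify multiple imputation with a complete-case sensitivity analysis. Use ANART only as an auxiliary variable: it is given at the study visit, after exposure, and so is not a clean sole basis for imputing a pre-war score.

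The cost is mainly wording. The downsides are some missing AFQT records to handle and one or two more model parameters.
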